11.1.6 Assessment of Adverse Events

All AEs and SAEs whether volunteered by the patient, discovered by study personnel during questioning, or detected through physical examination, laboratory test, or other means will be reported appropriately. Each reported AE or SAE will be described by its duration (i.e., start and end dates), regulatory seriousness criteria if applicable, suspected relationship to the study drug (see following guidance), and actions taken.

To ensure consistency of AE and SAE causality assessments, investigators should apply the following general guideline:

Unrelated:	No relationship between the experience and the administration of study device or drug; related to other etiologies such as concomitant medications or patient's clinical state.
Unlikely:	The current state of knowledge indicates that a relationship is unlikely.
Possibly Related:	A reaction that follows a plausible temporal sequence from administration of the study device or drug and follows a known response pattern to the suspected study material. The reaction might have been produced by the patient's clinical state or other modes of therapy administered to the patient.
Probably Related:	A reaction that follows a plausible temporal sequence from administration of the study device or drug and follows a known response pattern to the suspected study material. The reaction cannot be reasonably explained by known characteristics of the patient's clinical state or other modes of therapy administered to the patient.
Definite:	There is a definite relationship between the experience and the administration of study device or drug.

CONFIDENTIAL

STUDY DEVICE: SIR-Spheres®

SCRI INNOVATIONS STUDY NUMBER: GI 189

DATE OF ORIGINAL PROTOCOL: 16 December 2013

Date of Amendment #1: 15 April 2014

Version 2.0

11.2 Serious Adverse Event Reporting by Investigators

Adverse events classified by the treating investigator as serious require expeditious handling and reporting to SCRI Innovations Safety Department in order to comply with regulatory requirements. Determination of life-threatening or serious is based on the opinion of either the Sponsor or the Investigator.

Serious AEs may occur at any time from the start of study treatment through the 30 day period after the last dose of study drug. **The SCRI Innovations Safety Department must be notified of all SAEs, regardless of causality, within 24 hours of the first knowledge of the event by the treating physician or research personnel.**

To report a SAE, the SAE Report Form should be completed with the necessary information.

The SAE report should be sent to SCRI Innovations Safety Department via fax or e-mail using the following contact information (during both business and non-business hours):

SCRI Innovations Safety Department
Safety Dept. [contact]
Safety Dept. Email: [contact]

Transmission of the SAE report should be confirmed by the site personnel submitting the report.

Follow-up information for SAEs and information on non-serious AEs that become serious should also be reported to SCRI Innovations Safety Department as soon as it is available; these reports should be submitted using the SCRI Innovations SAE Report Form.

Investigators must report SAEs and follow-up information to their responsible Institutional Review Board (IRB) according to the policies of the responsible IRB.

11.3 Recording of Adverse Events and Serious Adverse Events

11.3.1 Diagnosis versus Signs and Symptoms

All AEs should be recorded individually in the patient's own words (verbatim) unless, in the opinion of the Investigator or designated physician, the AEs constitute components of a recognized condition, disease, or syndrome. In the latter case, the condition, disease, or syndrome should be named rather than each individual sign or symptom. If a constellation of signs and/or symptoms cannot be medically characterized as a single diagnosis or syndrome at the time of reporting, each individual event should be recorded as an AE or SAE as appropriate on the relevant form(s) (SAE Report Form and/or AE eCRF screen). If a diagnosis is subsequently established, it should be reported as follow-up information is available. If a diagnosis is determined subsequent to the reporting of the constellation of symptoms, the signs/symptoms should be updated to reflect the diagnosis.

Progression of malignancy (including fatal outcomes), if documented by use of appropriate method (for example, as per RECIST criteria for solid tumors), should not be reported as an SAE.

CONFIDENTIAL

STUDY DEVICE: SIR-Spheres®

SCRI INNOVATIONS STUDY NUMBER: GI 189

DATE OF ORIGINAL PROTOCOL: 16 December 2013

Date of Amendment #1: 15 April 2014

Version 2.0

11.3.2 Persistent or Recurrent Adverse Events

A persistent AE is one that extends continuously, without resolution, between patient evaluation time points. Such events should only be recorded once on the SAE Report Form and/or the AE eCRF screen. If a persistent AE becomes more severe or lessens in severity, it should be recorded on a separate SAE Report Form and/or AE eCRF screen.

A recurrent AE is one that occurs and resolves between patient evaluation time points, and subsequently recurs. All recurrent AEs should be recorded on an SAE Report Form and/or AE eCRF screen.

11.3.3 Abnormal Laboratory Values

If an abnormal laboratory value or vital sign is associated with clinical signs and/or symptoms, the sign or symptom should be reported as an AE or SAE, and the associated laboratory value or vital sign should be considered additional information that must be collected on the relevant eCRF screen. If the laboratory abnormality is a sign of a disease or syndrome, only the diagnosis needs to be recorded on the SAE Report Form or AE eCRF screen.

Abnormal laboratory values will be reported as an AE if: the laboratory result requires an adjustment in the study drug(s) or discontinuation of treatment, and/ or laboratory findings require additional testing or surgical intervention, a laboratory result or finding is associated with accompanying symptoms, or a laboratory result is considered to be an AE by the investigator.

11.3.4 Deaths

Deaths that occur during the protocol-specified AE reporting period that are attributed by the Investigator solely to progression of disease will be recorded on the “Study Discontinuation” eCRF screen. All other on study deaths, regardless of attribution, will be recorded on an SAE Report Form and expeditiously reported to the SCRI Innovations Safety Department.

When recording a SAE with an outcome of death, the event or condition that caused or contributed to the fatal outcome should be recorded as the single medical concept on the SAE Report Form and Adverse Event screen of the eCRF. If the cause of death is unknown and cannot be ascertained at the time of reporting, record “Death NOS” on the eCRF Adverse Event screen. During post-study survival follow-up, deaths attributed to progression of disease will be recorded only on the “After Progressive Disease Follow-Up” eCRF screen.

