8.1.3 Precautions and Risks Associated with SIR-Spheres® Microspheres

Overall, the incidence of complications after SIR-Spheres microspheres therapy, if patients are selected appropriately and target (i.e. liver) delivery is performed meticulously, is low.

Gastroduodenal complications occur in less than 10% of those treated (Bester et al. 2011; Kennedy et al. 2006; Stubbs et al. 2004) and are largely preventable.

A life-threatening complication, progressive pulmonary insufficiency secondary to radiation-induced lung fibrosis can be avoided by excluding from treatment with SIR-Spheres microspheres any patient with marked hepato-pulmonary shunting (Leung et al. 1995). There have been rare reported occurrences of this complication since that time.

The gallbladder also may receive SIR-Spheres microspheres through a patent cystic artery leading to radiation cholecystitis. In order to avoid this potential complication, infusion distal to the cystic artery is preferred, however the risk of radiation cholecystitis requiring cholecystectomy is low (Liu et al. 2005).

Gastric and duodenal ulceration have been reported to occur after the use of SIR-Spheres microspheres and are related to the inadvertent intestinal deposition of microspheres via extra-hepatic visceral arterial branches. Even in the absence of extra-hepatic activity on 99m Tc labelled MAA and Bremsstrahlung emission images, gastrointestinal symptoms have been reported to develop. The risk of gastrointestinal ulceration can be minimised with routine coil embolization of the extra-hepatic visceral arteries before infusion of SIR-Spheres microspheres (Liu et al. 2005).

Radioembolization induced liver disease (REILD) is a rare complication following selective internal radiation therapy (SIRT) with 90 Y microspheres. REILD is characterised by a well-defined constellation of temporal, clinical, biochemical and histopathologic findings. REILD typically manifests approximately 4-8 weeks post-SIRT and is characterised clinically by jaundice and ascites in the absence of tumour progression or bile duct obstruction. The typical biochemical picture of REILD is an elevated bilirubin (> 3 mg/dL) in almost all cases, elevated ALP and gamma-glutamyl transpeptidase (GGT) in most cases, accompanied by virtually no change in the transaminases (AST and ALT). In the event that a liver biopsy is performed, the typical histological appearance is of sinusoidal obstruction that may resemble veno-occlusive disease.

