10.4.3 Early Safety Monitoring and Stopping Rules

A safety review for toxicity by the Medical Monitor will occur after the first 10 patients have been enrolled in each cohort and treated with one cycle of regorafenib and SIR-spheres (combination therapy) to assess the frequency of \geq Grade 3 adverse events and all SAEs. Accrual will not be halted while the analysis is being conducted.

Stopping Rules Due to Toxicities of Combination Therapy

Stopping rules due to toxicities assessed as related to combination therapy by the Medical Monitor will be defined as follows:

- A patient death considered to be caused by AEs of combination therapy

CONFIDENTIAL

STUDY DEVICE: SIR-Spheres®

DATE OF ORIGINAL PROTOCOL: 16 December 2013

Date of Amendment #1: 15 April 2014

SCRI INNOVATIONS STUDY NUMBER: GI 189

Version 2.0

- A patient with Grade 4 AST, ALT, or irreversible hepatic failure assessed as related to combination therapy;
- More than 2 patients that develop Grade 3 AST, ALT, or total bilirubin assessed as related to combination therapy;
- More than 2 patients develop Grade 3 bleeding in the lung, stomach, small intestine, or liver assessed as related to combination therapy.

If the early stopping rules are met or safety signals emerge from the group of the first 10 patients treated with combination therapy in each cohort, patient recruitment will discontinue and the study will be reassessed. Any outcome of these safety reviews will be communicated in a timely manner to the participating investigators so that they may notify their IRBs.

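### Deaths attributed solely to progression skip SAE reporting under 11.3.4 without the documentation 11.3.1 requires, and have no required route to the Medical Monitor who judges the one-death stopping rule

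*Protocol*

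**What the plan says.** Two sections of the protocol decide whether a death from cancer is reported as an SAE.

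- **Section 11.3.1** starts from "Progression of malignancy (including fatal outcomes), if documented by use of appropriate method" and withholds SAE reporting on a condition: "if documented by use of appropriate method (for example, as per RECIST criteria for solid tumors), should not be reported as an SAE".
- **Section 11.3.4** covers the adverse event reporting period. Its first sentence reads, in part: "Deaths that occur during the protocol-specified AE reporting period that are attributed by the Investigator solely to progression of disease will be recorded on". Study Discontinuation is the eCRF screen named. For the rest: "All other on study deaths, regardless of attribution, will be recorded on an SAE Report Form and expeditiously reported" to the sponsor's safety department. For later deaths: "During post-study survival follow-up, deaths attributed to progression of disease will be recorded only on the" post-progression follow-up screen. In that last sentence the word solely is absent.

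The first stopping rule in Sections 5 and 10.4.3 is "A patient death considered to be caused by AEs of combination therapy". The same sections give the relatedness judgement to the Medical Monitor. They define the review, after the first 10 patients in each cohort have been treated with the combination, as an assessment of Grade 3 or higher adverse events and all SAEs.

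Section 11.3.7 adds that symptoms of metastasis are to be treated as disease progression and not reported as AEs or SAEs.

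Section 8.1.3 describes radioembolization-induced liver disease (REILD) as appearing about 4 to 8 weeks after treatment, "characterised clinically by jaundice and ascites in the absence of tumour progression or bile duct obstruction".

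**The concern.** The primary objective is safety, and a single death can stop recruitment. Under 11.3.4, the investigator's opinion that a death was due solely to progression is enough to keep it off an SAE form. No scan or other evidence is required, and nobody is assigned to check the opinion. The person who must decide whether a death was caused by the combination is given a data set in which that death need not appear.

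The gate works in one direction. A progression death wrongly put down to treatment goes on an SAE form and can be corrected at review. A treatment death wrongly put down to progression drops out of the SAE stream. Any error from this source therefore lowers the apparent treatment-related mortality.

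The setting makes such an error plausible. All patients have liver metastases, and both treatments carry liver risk: REILD in Section 8.1.3, and fatal drug-induced liver injury with regorafenib in Section 6.2.1. By the protocol's own description, REILD is told apart from tumour progression by showing that progression is absent.

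**Working it through.** No figure in the plan is at stake, so the main check sets the provisions side by side.

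**1. The gate for SAE reporting**

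| Death in the AE reporting period | 11.3.1 | 11.3.4 |
|---|---|---|
| Attributed solely to progression, progression documented | no SAE | no SAE form |
| Attributed solely to progression, progression not documented | exemption not available | no SAE form |
| Mixed, unknown or other cause | exemption not available unless fatal progression is documented | SAE form |

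The sections diverge in the second row. A site following 11.3.4 literally files nothing for a death that 11.3.1 does not exempt.

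**2. The route from that row to the Medical Monitor**

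- The review inputs are Grade 3 or higher AEs and all SAEs. An entry on the Study Discontinuation screen is neither.
- The preceding jaundice or ascites could reach the review as a Grade 3 or higher AE. If the investigator regards it as a symptom of metastasis, however, 11.3.7 removes it on the same judgement that removed the death.
- Nothing in either document requires the discontinuation screen to be sent to the Medical Monitor.
- The SAP adds no second look. The box for an independent DMC/DSMB is unticked, the only adverse event table listed is Table 8 (treatment-related events), and no deaths table is listed.

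**3. Whether documentation could be missing**

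The first scheduled restaging is 6 weeks after SIR-Spheres (Section 7.5), inside the 4 to 8 week window for REILD. A patient who dies before it, and before an End-of-Treatment CT, may have no post-treatment scan.

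**4. Illustration of what is at stake for the death rule**

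Assumptions, none from the documents: patients are independent, each has probability *p* of a treatment-related death, a share *m* of those deaths is attributed to progression and not seen, and every death that is seen is judged correctly. For *n* = 10:

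P(rule fires) = 1 − (1 − *p*(1 − *m*))^10

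For *p* = 5% and *m* = 50%: 1 − (1 − 0.025)^10 = 22.4%.

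| *p* | *m* = 0 | *m* = 25% | *m* = 50% |
|---|---|---|---|
| 2% | 18.3% | 14.0% | 9.6% |
| 5% | 40.1% | 31.8% | 22.4% |
| 10% | 65.1% | 54.1% | 40.1% |

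**5. Whether early deaths needing attribution are plausible**

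Assume exponential survival with the 6.4-month median on regorafenib quoted in the Introduction. All-cause death by 6 weeks is 1 − 2^(−(42/30.44)/6.4) = 13.9%. With medians of 5.0 and 10.0 months, also quoted in the protocol, it is 17.4% and 9.1%. These are on the high side, because entry requires a life expectancy of at least 3 months. They show only that early deaths will probably need attributing.

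**The case against.** There is a fair case that the gap is narrow.

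- **Solely.** The exemption in the AE period does not cover every death linked to progression. Mixed or contributory cases go on an SAE form, and an unascertained cause is recorded as Death NOS on the Adverse Event screen. This stands, and it rules out the stronger reading that any death the investigator connects with progression escapes. It still leaves an unverified opinion as the gate.
- **Reading the sections together.** 11.3.1 can be taken to say when fatal progression is not an SAE, and 11.3.4 to say which screen records it. That may be the intention. But 11.3.4 does not say so, and its sentence on all other deaths makes attribution the only test.
- **Other routes.** Section 11.1.5 asks for all AEs regardless of relationship, and Section 11.3.5 makes an AE that leads to hospitalization an SAE. Sections 11.1.2 and 11.2 let the sponsor's view count on seriousness. The End-of-Treatment visit includes CT and chemistry. Section 13.4 has the eCRF kept current for sponsor review. These routes are real, so a reader should not infer that the Medical Monitor will never learn of such a death. None is a requirement that the death reach the review, and 11.3.7 can close the first two.
- **Distinguishability.** Section 8.1.3 gives REILD a typical biochemical picture: bilirubin above 3 mg/dL, raised ALP and GGT in most cases, and virtually unchanged transaminases. The documents do not support a claim that REILD, regorafenib injury and tumour progression are indistinguishable. They do make absence of progression part of the clinical description, and showing that needs imaging.
- **Size.** A reader might take the share of patients dying before the first post-treatment scan as the size of the problem: about 14% at 6 weeks in Cohort 2 and 22% at 10 weeks in Cohort 1. That does not follow. Those are all-cause deaths under an assumed model. Cohort 1's 10 weeks include 4 weeks before SIR-Spheres, when no death can be due to the combination. In Cohort 2 a 2-week rest plus a 28-day cycle takes 6 weeks, so a patient who dies earlier may not count among the ten reviewed. On the same model, deaths between weeks 4 and 6 are about 4.4% (13.9% − 9.5%), and these too are all-cause.
- **Overall survival** counts every death whatever its attribution. This stands. What can be lost is the attribution to treatment, not the death itself.

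**Conclusion.** The inconsistency between 11.3.1 and 11.3.4 is real and should be corrected. An undocumented death attributed solely to progression is exempt under one section and not under the other. If the attribution is wrong, the death has no required route to the Medical Monitor's review. It may still be seen through other recorded events or the eCRF, so this is a gap in the plan and not a certainty that a death will be missed.

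The frequency of misattribution cannot be estimated from the documents. The illustration shows how sensitive a one-death rule is. Across assumed treatment-related death rates of 2% to 10%, missing a quarter to a half of such deaths lowers the chance of the rule firing in 10 patients by about 4 to 25 percentage points (18.3% to 14.0% at the low end, 65.1% to 40.1% at the high end). These figures rest wholly on the assumed rates and shares. The conclusion itself rests on the wording of Sections 5, 10.4.3, 11.3.1, 11.3.4 and 11.3.7, and does not depend on them.

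**What to change.** Two changes to the protocol:

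1. **Reconcile 11.3.4 with 11.3.1.** Carry 11.3.1's own condition into 11.3.4: within the AE reporting period, a death attributed solely to progression goes to the Study Discontinuation screen only if the progression is documented by an appropriate method, for example RECIST. A death without such documentation is reported on an SAE form. An exemption limited to RECIST imaging would be stricter than 11.3.1 and is not needed for consistency.
2. **Complete the review in Sections 5 and 10.4.3.** State that the Medical Monitor's review includes a listing of all on-study deaths, whatever the investigator's attribution, with the last available liver tests and scan for each. This is needed even if 11.3.1 was always meant to govern 11.3.4, because whoever applies a one-death rule should see every death.

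The cost is protocol wording, some additional SAE forms, and one listing from data already collected. The downside is that some deaths truly due to progression will be handled as SAEs. No dose, treatment rule or stopping threshold changes.

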11.3.5 Hospitalization, Prolonged Hospitalization, or Surgery

Any AE that results in hospitalization or prolongation of pre-existing hospitalization should be documented and reported as an SAE unless specifically instructed otherwise in this protocol. There are some hospitalizations that do not require reporting as an SAE.

Treatment within or admission to the following facilities is not considered to meet the criteria of “inpatient hospitalization” (although if any other SAE criteria are met, the event must still be treated as an SAE and immediately reported):

- Emergency Department or Emergency Room

CONFIDENTIAL

STUDY DEVICE: SIR-Spheres®

SCRI INNOVATIONS STUDY NUMBER: GI 189

DATE OF ORIGINAL PROTOCOL: 16 December 2013

Date of Amendment #1: 15 April 2014

Version 2.0

- Outpatient or same-day surgery units
- Observation or short-stay unit
- Rehabilitation facility
- Hospice or skilled nursing facility
- Nursing homes, Custodial care or Respite care facility

Hospitalization during the study for a pre-planned surgical or medical procedure (one which was planned prior to entry in the study), does not require reporting as a SAE to the SCRI Innovations Safety Department.

11.3.6 Pre-Existing Medical Conditions

A pre-existing medical condition is one that is present at the start of the study. Such conditions should be recorded on the General Medical History eCRF screen. A pre-existing medical condition should be recorded as an AE or SAE only if the frequency, severity, or character of the condition worsens during the study. When recording such events on an SAE Report Form and/or AE eCRF screen, it is important to convey the concept that the pre-existing condition has changed by including applicable descriptors.

11.3.7 New Cancers

The development of a new primary cancer should be regarded as an AE and will generally meet at least one of the seriousness criteria (see Section 11.1.2). New primary cancers are those that are not the primary reason for the administration of the study treatment and have developed after the inclusion of the patient into the study. They do not include metastases of the original cancer. Symptoms of metastasis or the metastasis itself should not be reported as an AE/SAE, as they are considered to be disease progression.

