10.4.2 Efficacy Analysis

All efficacy analyses will be performed using the Intent-To-Treat Population.

- Overall Response Rate (ORR) is defined as the proportion of patients with observed CR or PR (i.e. 2 CRs or PRs at least 4 weeks apart) according to the RECIST 1.1 criteria.
- Progression Free Survival (PFS), defined as the time from the first day of study drug administration (Day 1) to disease progression as defined by the RECIST v1.1 criteria, or death on study. Patients who are alive and free from disease progression will be censored at the date of last adequate tumor assessment.
- Overall Survival (OS), defined as the time from the first day of study drug administration (Day 1) to death. Patients who are alive will be censored at the date of last known date alive.

For ORR, the estimates and the associated 95% confidence interval (based on the Clopper-Pearson method) in each treatment group will be calculated.

For PFS and OS, Kaplan-Meier curves will be generated and the median time to event and the associated 95% confidence interval will be provided.

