11.1 Definitions

11.1.1 Adverse Events

Adverse event means any untoward medical occurrence associated with the use of a drug in humans, whether or not considered drug related. An adverse event (also known as adverse experience) can be any unfavorable and unintended sign (e.g., an abnormal laboratory finding), symptom, or disease temporarily associated with the use of a drug, without any judgement about causality. An adverse event can arise with any use of the drug (e.g., off-label use, use in combination with another drug) and with any route of administration, formulation, dose or including overdose.

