All AEs regardless of seriousness or relationship to regorafenib and/or SIR-Spheres treatment (called study treatment), spanning from the start of study treatment, until 30 calendar days after discontinuation or completion of study treatment as defined by the clinical study for that patient, are to be recorded on the corresponding screen(s) included in the eCRF.

All AEs resulting in discontinuation from the study should be followed until resolution or stabilization. All new AEs occurring during this period must be reported and followed until resolution unless, in the opinion of the investigator, the AE or laboratory abnormality/ies are not likely to improve because of the underlying disease. In this case, the investigators must record his or her reasoning for this decision in the patient's medical record and as a comment on the eCRF screen.

After 30 days of completion of protocol-specific treatment or discontinuation, only AEs, SAEs, or deaths assessed by the investigator as treatment related are to be reported.

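### Section 11.3.7 keeps symptoms of metastasis out of AE and SAE reporting without requiring documented progression, in conflict with Sections 11.3.1, 11.1.5 and 11.3.6

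*Protocol*

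**What the plan says.** The exemption is the last sentence of Protocol Section 11.3.7 (New Cancers): "Symptoms of metastasis or the metastasis itself should not be reported as an AE/SAE, as they are considered to be disease progression".

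Other parts of Section 11 set different boundaries:

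- Section 11.1.1: "Adverse event means any untoward medical occurrence associated with the use of a drug in humans, whether or not considered drug related".
- Section 11.1.5, reporting period: the eCRF takes "All AEs regardless of seriousness or relationship to regorafenib and/or SIR-Spheres treatment". The same section says that clinically significant signs and symptoms are reported as AEs.
- Section 11.3.1: progression of the malignancy, "if documented by use of appropriate method (for example, as per RECIST criteria for solid tumors), should not be reported as an SAE".
- Section 11.3.6: a condition present at the start of the study becomes an AE or SAE if its frequency, severity or character worsens.

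The primary objective is safety (Section 2.1). Section 10.4.4 assesses it through the reported incidence of treatment-emergent AEs, with further summaries of SAEs and of AEs leading to discontinuation. Section 10.4.3 has the Medical Monitor review Grade 3 or higher AEs and all SAEs once the first 10 patients in each cohort have been treated. Inclusion criterion 5 requires measurable liver metastases in every patient.

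**The concern.** The main safety measure depends on what sites enter, and the protocol gives them more than one rule for the same event. Two sites could each follow the protocol and treat the same episode of jaundice differently. One would record it, grade it and attribute it to the tumour; the other would record nothing.

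The population makes this more than a matter of wording. All patients have liver metastases, and Section 8.1.3 lists treatment effects that can look like them: abdominal pain and lethargy after the procedure, and a radioembolization liver disease "characterised clinically by jaundice and ascites in the absence of tumour progression or bile duct obstruction". If a site attributes such a sign to metastasis without checking, Section 11.3.7 stops it before it reaches the database.

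Recording an event as unrelated leaves it open to re-assessment. Not recording it removes it from the Medical Monitor's review and, if serious, from the reports sent to the device manufacturer for a causality opinion (Section 11.4). The rule can only remove events, so any bias is towards apparent safety, in a study with no control group.

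**Working it through.** No stated figure is in dispute. The check compares the rules and then gives the size per patient.

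**1. The rules side by side**

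| Section | What is exempt or recorded | From AE reporting? | From SAE reporting? | Documentation required? |
|---|---|---|---|---|
| 11.1.1, 11.1.5 | All AEs, whatever the relationship | Recorded | Reported if serious | Not applicable |
| 11.3.6 | Pre-existing condition that worsens | Recorded | Reported if serious | Not applicable |
| 11.3.1 | Progression of malignancy | Not exempt | Exempt | Yes, for example RECIST |
| 11.3.7 | Symptoms of metastasis, or the metastasis | Exempt | Exempt | None stated |

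Sections 11.3.1 and 11.3.7 differ in both scope and condition.

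**2. A test case**

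Take a patient with new ascites and jaundice in week 5 after SIR-Spheres, admitted to hospital, with no scan since baseline. The site believes that the liver metastases are responsible.

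- Under 11.1.1 and 11.1.5 this is an AE, entered with the site's attribution.
- Under 11.3.6 a worsened pre-existing condition is recorded.
- Under 11.3.1 no exemption applies, because progression has not been documented.
- Under 11.3.7 it is neither an AE nor an SAE.
- Section 11.3.5 would make the admission an SAE, but gives way to any specific contrary instruction elsewhere in the protocol. Section 11.3.7 can be read as one.

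**3. Is a current scan likely to be available?**

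Baseline CT may be up to 28 days before treatment (Section 7.1). In Cohort 1, SIR-Spheres follows 21 days of regorafenib and a 1-week washout, so 28 days after the start. The first restaging CT is 6 weeks (42 days) after SIR-Spheres (Section 7.5). The nominal gap between scheduled scans is:

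- Cohort 1: 0 + 28 + 42 = 70 days to 28 + 28 + 42 = 98 days.
- Cohort 2: 0 + 42 = 42 days to 28 + 42 = 70 days.

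Section 8.1.3 puts the typical onset of radioembolization liver disease at about 4 to 8 weeks, so some cases would appear before the Week 6 scan. An unscheduled scan is possible, but Section 11.3.7 does not ask for one.

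**4. Size**

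One omitted patient in a cohort of 25 is 1/25 = 4 percentage points. The documents give neither the true event rate nor the share that would be attributed to metastasis, so both are assumptions here. With true rate p and omitted share d, the reported rate is p(1 − d):

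| Assumed p | d = 0 | d = 25% | d = 50% |
|---|---|---|---|
| 20% | 20% | 15% | 10% |
| 30% | 30% | 22.5% | 15% |
| 40% | 40% | 30% | 20% |

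For single patients, with exact (Clopper-Pearson) 95% intervals: 5/25 is 20% (6.8% to 40.7%), 4/25 is 16% (4.5% to 36.1%) and 3/25 is 12% (2.5% to 31.2%). Losing one or two patients shifts the estimate by 4 or 8 points, and the interval does not account for that shift.

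**5. What the laboratory data still catch**

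Chemistry is scheduled in both cohorts (Sections 7.3 and 7.4). Under Sections 11.1.5 and 11.3.3, an abnormal result is an AE if it requires a study drug adjustment, discontinuation or additional testing. Laboratory data are summarised separately (Protocol 10.4.4; SAP Section 7). This protects AST, ALT and bilirubin. It is partial, because 11.3.3 also lets a diagnosis stand in for the laboratory sign, and ascites, pain and lethargy have no laboratory counterpart.

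**The case against.** The sentence closes a paragraph that separates new primaries from metastases of the original cancer. Its stated reason, that such symptoms count as progression, suggests that worsening was assumed. Sections 11.1.5 and 11.3.6 would lead a careful site to record a hepatic sign not shown to be progression. That is a fair account of the probable intent. But the wording covers symptoms as well as lesions, and it deems them progression rather than asking for evidence.

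Ascites is excluded at entry (exclusion criterion 9) and bilirubin is capped at 1.5 × ULN, apart from Gilbert-type cases (inclusion criterion 8). On-study jaundice or ascites would therefore usually be new and noticeable. This makes omission less likely, but 11.3.7 does not depend on whether the symptom is new.

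Three stronger readings are tempting and not supported:

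- **That only absence of progression separates radioembolization liver disease from tumour.** Section 8.1.3 also uses timing, bilirubin and other biochemistry, bile duct status and histology, and the Week 6 CT falls inside the typical onset window.
- **That the stopping rules would trigger less often by a calculable amount.** The hepatic rule for more than 2 patients counts related Grade 3 AST, ALT or total bilirubin, which scheduled chemistry still captures. No rule counts abdominal pain, ascites or clinical jaundice.
- **That these events also disappear from PFS.** PFS runs "to disease progression as defined by the RECIST v1.1 criteria, or death on study". That is a coherent definition, and scheduled and end-of-treatment CT would still detect RECIST progression.

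Finally, the only AE table listed in the SAP (Table 8) covers treatment-related AEs. A symptom attributed to metastasis would be absent from it even if recorded. This limits where the correction shows, but does not remove the need for it.

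**Conclusion.** The conflict is real and in the current text. Followed as written, Section 11.3.7 lets an unverified site attribution keep non-laboratory clinical events out of the all-cause and SAE summaries in Section 10.4.4 and out of the Medical Monitor's review. The bias can only run towards apparent safety, at 4 percentage points per omitted patient in a cohort of 25.

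The loss is possible, not certain: it requires a site to attribute the event to metastasis and to apply 11.3.7 over the other sections. The rates and shares in the working are assumptions, and a share of zero gives no loss. The laboratory-based hepatic stopping rule is largely unaffected, and no change in its trigger probability should be claimed. The point concerns non-fatal events. It should be corrected, because the remedy is small and the measure affected serves the primary objective.

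**What to change.** Reconcile Section 11.3.7 with Section 11.3.1 so that both state one scope and one condition:

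- Only progression, or a new metastatic lesion, documented by an appropriate method such as RECIST 1.1 is not itself reported as an AE or SAE.
- The associated signs, symptoms and diagnoses are recorded as AEs with grade and attribution under Section 11.1.5, including those thought to be due to metastases. They are reported as SAEs if a seriousness criterion is met.

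If the sponsor meant only to separate metastases from new primaries, the revised sentence should say so. The benefit appears in the all-cause and SAE summaries promised in Section 10.4.4 and in the Medical Monitor's review, not in SAP Table 8.

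The cost is a short wording change, somewhat more AE and SAE entry, and slightly higher reported all-cause AE rates. No dose, visit or clinical rule changes.
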